8.1.1. Incidence of Adverse Events

All AEs will be presented in a data listing, and all TEAEs will be presented in a summary table by SOC, PT treatment group and overall. Additional table of TEAEs will be presented in a summary by PT only.

An overall summary table will be created presenting the number of events and percentage of subjects with:

- Any TEAE
- Any study-drug-related TEAE
- Any severe TEAE
- Any severe study-drug-related TEAE
- Any serious adverse event (SAE)
- Any treatment-emergent, study-drug-related SAE
- Any AE leading to early study discontinuation
- Any DLT
- Any death

The definition of DLT is defined in [Section 8.1.6](#). For the purpose of above summary, a study-drug-related or ticagrelor-related AE is an AE with definite, probable, possible, or missing relationship to the study drug or ticagrelor respectively on eCRF.

8.1.2. Severity of Adverse Event

The severity (or intensity) of an AE refers to the extent to which it affects the subject's daily activities and will be classified as mild, moderate, or severe. The TEAEs will be summarized by SOC, PT, severity (including category 'Missing' for events with missing severity assessment on eCRF) and treatment group. A subject with 2 or more TEAEs within the same level of summarization with at least 2 different non-missing severities will be counted only once using the most severe AE.

The Common Terminology Criteria for Adverse Event (CTCAE) v5 grading scale will be used by the SRC to assess all infusion-related reactions for the purposes of determining whether premedication to mitigate future potential infusion-related reactions is required for subsequent study subjects. Details of infusion-related reactions are provided in [Section 8.1.5](#) Additionally, CTCAE v5 will be used by the SRC to assess all AEs and laboratory

abnormalities for the purposes of determining whether a DLT and/or stopping criteria have been reached. Details of the definition of DLT are provided in [Section 8.1.6](#).

8.1.3. Relationship of Adverse Events to Study Drug

The relationship of AE to study drug and ticagrelor (if applicable) will be classified by the Investigator as unrelated, possible, probable, and definite. TEAEs will be summarized by SOC, PT, relationship to PB2452 and ticagrelor (if applicable), including category 'Missing', and treatment group. A subject with 2 or more TEAEs within the same level of summarization will be counted only once in that level using the most related incident.

8.1.4. Adverse Events Leading to Early Discontinuation

All AEs that lead to early discontinuation will be presented in a listing.

8.1.5. Infusion Site Assessments

The infusion site will be examined by the investigator or designee for pain, tenderness, erythema/redness, and induration/swelling at Day 1 (within 15 minutes prior to the initiation of the MEDI2452 [PB2452] infusion [Hour 0], and at 1, 3 hours after initiation of the MEDI2452 [PB2452] infusion), at Day 2, Day 3, Day 4 and Day 7.

The infusion site assessments will not be recorded in the database and will only be kept in the source documents. Any infusion-related reaction will be documented as an AE for each individual symptom. The individual symptom will be noted in the AE comments data field. Assessment of severity of the infusion-related reactions be classified as mild, moderate, or severe, and will also be assessed according to CTCAE v5 grading scale and should be followed until resolution.

8.1.6. Dose Limiting Toxicities

The SRC will review all AEs and all laboratory and ECG abnormalities according to CTCAE v5 to determine whether a DLT has been identified in a subject who is confirmed to have received MEDI2452 (PB2452). If the SRC determines that an AE is related to

administration of ticagrelor (Cohorts 4-10), or another confirmed cause, the AE will not be considered a DLT.

The SRC will provide an external spreadsheet which contains all DLT events and this external spreadsheet will be used in the summaries and listings.

Definitions for DLT are described below:

1. A DLT is defined as any AE that is assessed as grade 2 or higher based on the CTCAE v5 grading scale and has occurred in a subject confirmed to have received MEDI2452 (PB2452).
2. A DLT is defined as any grade 2 or higher laboratory abnormality (outside the clinical laboratory normal reference range) that occurs in a subject confirmed to have received MEDI2452 (PB2452). [Note: For a grade 2 electrolyte abnormality that spontaneously resolves to \leq grade 1 (without intervention) within 24 hours, the SRC may decide to exempt the laboratory abnormality from being considered a DLT].
3. A DLT is defined as any TEAE that leads to study withdrawal of a subject confirmed to have received MEDI2452 (PB2452).

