8.1. Adverse Events

An AE is defined as any untoward medical occurrence associated with the use of a drug in humans, whether or not considered drug-related.

A TEAE is defined as any event not present before exposure to study drug or any event already present that worsens in intensity or frequency after the exposure. For analysis purposes, TEAEs are the events with onset on or after initiation of study drug.

Adverse events will be coded using the Medical Dictionary for Regulatory Activities (MedDra), version 21.0 or higher, by system organ class (SOC) and preferred term (PT).

All summary tables except from the overall summary table will be based on TEAEs. The SOCs will be displayed in descending order of overall frequency and then alphabetically. The PTs will be displayed in descending order of overall frequency and then alphabetically within SOC. A subject with 2 or more AEs within the same level of summarization will be counted only once in that level using the most severe (for the severity table) or most related (for the relationship to study drug table) incident.

Summary tables will be presented by treatment groups as defined in [Section 4.1](#). Percentages will be based upon the number of subjects in the safety population overall and within each treatment group.

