Additional PD parameters may be calculated, as necessary. Pharmacodynamic parameters will be listed by subject and summarized for each cohort using descriptive statistics (number of subjects, mean, SD, median, minimum, and maximum).

12. Changes in the Planned Analysis

For ECG measurements, QTcB interval will be calculated and a summary table for QTcF and QTcB values outside of pre-defined criteria will be produced.

13. Interim Analysis

There's no planned formal interim analysis for this study. Blinded safety data review for each dose cohort will be performed before dosing in the next cohort is allowed (Section 3.4.2.1 of the protocol).

Interim noncompartmental analyses of PK data and/or PK/PD modeling will be performed as needed.

14. Reference

Memo Re: PB2452-PT-CL-0001 Cohort 7 Dosing Regimen. To: [name], Principal Investigator, PPD Early Development Services; [name], Associate Director, Project Management, PPD Early Development. CC: [name], Project Manager, PPD Early Development. From: [name], Director, Clinical Operations. Date: July 3, 2018.

Memo Re: PB2452-PT-CL-0001 Cohort 8 Dosing Regimen. To: [name], Principal Investigator, PPD Early Development Services; [name], Associate Director, Project Management, PPD Early Development. CC: [name], Project Manager, PPD Early Development. From: [name], Director, Clinical Operations. Date: July 25, 2018.

Memo Re: PB2452-PT-CL-0001 Cohort9 and 10 Dosing Regimens. To: [name], Principal Investigator, PPD Early Development Services; [name], Associate Director, Project Management, PPD Early Development. CC: [name], Project Manager, PPD Early Development. From: [name], Sponsor Medical Consultant. Date: August 8, 2018.

15. Table of Contents: Tables, Listings and Figures

List of Tables	
Subject Disposition	
Table 14.1.1.	Subject Disposition
Demographics and Baseline Characteristics	
Table 14.1.2	Demographic and Baseline Characteristics (Safety Population)
Pharmacokinetics	
Table 14.2.1.1	Summary of Total Plasma PB2452 Concentrations (unit) (PK Population)
Table 14.2.1.2	Summary of Unbound Plasma PB2452 Concentrations (unit) (PK Population)
Table 14.2.1.3	Summary of Total Plasma Ticagrelor and AR-C124910XX Concentrations (unit) (PK Population)
Table 14.2.1.4	Summary of Unbound Plasma Ticagrelor and AR-C124910XX Concentrations (unit) (PK Population)

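### SAP 8.1.6 allows a DLT only in subjects confirmed to have received PB2452, yet 'Any DLT' is tabulated for the placebo groups too, where it is zero by definition

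*SAP*

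**What the plan says.** **Definition.** Under SAP 8.1.6 the SRC reviews all adverse events and all laboratory and ECG abnormalities by CTCAE v5, "to determine whether a DLT has been identified in a subject who is confirmed to have received MEDI2452 (PB2452"). Each definition carries the same restriction:

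- an adverse event of grade 2 or higher that "has occurred in a subject confirmed to have received MEDI2452 (PB2452");
- a laboratory abnormality of grade 2 or higher "that occurs in a subject confirmed to have received MEDI2452 (PB2452"), with a possible exemption for grade 2 electrolyte changes that resolve within 24 hours;
- "any TEAE that leads to study withdrawal of a subject confirmed to have received MEDI2452 (PB2452").

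If the SRC attributes an event to ticagrelor, "or another confirmed cause, the AE will not be considered a DLT".

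**Reporting.** The SRC supplies a spreadsheet of DLT events, and "this external spreadsheet will be used in the summaries and listings". SAP 8.1.1 lists 'Any DLT' as a row of the overall adverse event table (Table 14.3.1.1). SAP 8.1 sets the columns: "Summary tables will be presented by treatment groups as defined in" Section 4.1. That section lists Placebo C1-C3, Placebo C4-C6, Placebo C7-C10, All Placebo, All PB2452 and All subjects. Percentages use the safety population, overall and within each group.

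**Blinding.** SAP 13 states: "Blinded safety data review for each dose cohort will be performed before dosing in the next cohort is allowed". SAP 4.4 allows a subject to be unblinded in the event of a DLT.

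**The concern.** A row shown side by side for active and placebo groups invites comparison. Here the comparison is empty, because a placebo subject with the same grade 2 event as an active subject cannot be counted. The DLT threshold is low (any grade 2 event or laboratory value), so some background events in confined healthy volunteers are plausible. A reader of the table would see DLTs on PB2452 and none on placebo and could take this for a treatment difference, although the placebo side was fixed in advance. Safety and tolerability is a primary objective, and the overall adverse event table is where many readers will look first.

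A second, smaller matter is that the DLT count depends on SRC judgements of grade and cause. SAP 8.1.6 does not say how these fit with the blinded cohort review of SAP 13.

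**Working it through.** **1. Group sizes.** From SAP Table 3-1, with Cohorts 9 and 10 at 6:2:

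- active = 3×3 + 5×6 + 2×6 = 51
- placebo = 3×1 + 5×2 + 2×2 = 17
- total = 68, which reproduces the maximum in SAP 4.2.

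If Cohorts 9 and 10 stay at 3:1, active = 45, placebo = 15 and total = 60.

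**2. The placebo cells.** All three definitions require confirmed PB2452, and the spreadsheet is the source of the row. The count is therefore 0 of 3 (C1-C3), 0 of 6 (C4-C6), 0 of 6 to 8 (C7-C10) and 0 of 15 to 17 (All Placebo), regardless of what occurred.

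**3. The all-subjects cell.** If *x* active subjects have a DLT, the All PB2452 percentage is *x*/51 and the all-subjects percentage is *x*/68. Their ratio is 51/68 = 0.75 (or 45/60 = 0.75). The lower figure arises only because a quarter of the denominator cannot have the event.

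**4. What the zeros could hide.** The documents give no background rate, so *q*, the proportion of subjects with a qualifying event unrelated to PB2452, is an assumption. The expected count is *nq*, and the probability of at least one is 1 − (1 − *q*)^*n*.

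| Assumed *q* | Expected among 15 / 17 placebo | P(at least one) among 15 / 17 placebo | Expected among 45 / 51 active | P(at least one) among 6 active |
|---|---|---|---|---|
| 5% | 0.75 / 0.85 | 0.537 / 0.582 | 2.25 / 2.55 | 0.265 |
| 10% | 1.5 / 1.7 | 0.794 / 0.833 | 4.5 / 5.1 | 0.469 |
| 20% | 3.0 / 3.4 | 0.965 / 0.977 | 9.0 / 10.2 | 0.738 |

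The active columns assume no drug effect and are taken before the SRC removes events with another cause or exempts electrolyte changes, so the reported DLT count would be lower. The placebo count in the table is 0 in every row.

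**5. Whether another table fills the gap.** SAP 8.1.2 grades TEAEs as mild, moderate or severe for the severity table and describes CTCAE v5 as a tool of the SRC. SAP 8.2 plans actual values, changes and shifts for laboratory tests. The overall table also has rows for severe TEAEs and for adverse events leading to early study discontinuation. The last is close to the third DLT definition without the treatment condition. All of these are shown by arm. None uses the CTCAE grade 2 cut, and the list of tables in SAP 15 has no CTCAE-graded output.

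**6. The order of grading, attribution and unblinding.** SAP 8.1.6 states none. SAP 13 describes the cohort review as blinded. SAP 4.4, and section 3.4.2.1 of the supplied protocol, allow unblinding once a DLT is in question. Two DLT definitions in protocol 3.4.2.3 refer to confirmation after unblinded review. Blinded judgement followed by unblinding fits these texts, and so does judgement with assignment known.

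**The case against.** **DLT is an escalation term.** Limiting it to active drug can be deliberate, and protocol 3.4.2.3 already does so in two of its definitions. The adverse event tables are descriptive and no active-versus-placebo test of DLTs is planned. This stands, and it is why the definition itself need not change. It does not justify printing placebo cells that can only be zero.

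**Placebo safety data are reported elsewhere.** A reader might infer that the randomized control for background events has been lost. The documents do not support that: TEAEs by severity and relationship, discontinuations and laboratory shifts are all tabulated by arm. What is missing is narrower, namely events at the CTCAE grade 2 cut by arm.

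**Attribution with treatment known.** A reader might also infer from SAP 8.1.6 that the SRC judges cause only in subjects whose active assignment it already knows. The text does not establish this. The section gives no sequence and opens with a review of all events. SAP 13 describes blinded review, and SAP 4.4 lets unblinding follow a suspected DLT. Only the weaker statement holds: a DLT cannot be finally declared without the assignment, and the SAP does not say when grade and cause are judged.

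**Amendment 5 is not available.** The SAP reflects protocol amendment 5 of 03 August 2018, and the supplied protocol is dated 01 Feb 2018. The amendment may state the order. It would not change what SAP 8.1, 8.1.1 and 8.1.6 do to the table.

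**Conclusion.** The reporting defect follows from the SAP text alone. 'Any DLT' is zero by definition in all four placebo columns, and the all-subjects percentage is 0.75 times the All PB2452 percentage. The 0.75 assumes that the Table 3-1 allocation is realised in the safety population. How much background the zeros would conceal is not known from the documents. At assumed rates of 5% to 20%, between 0.75 and 3.4 placebo subjects would be expected to meet the criteria, with a probability of at least one between 0.54 and 0.98. Other tables give partial background but not at the DLT threshold.

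The order of attribution and unblinding is a gap in the text and not a demonstrated bias. It calls for the sections to be reconciled and supports no stronger conclusion.

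**What to change.** 1. In Table 14.3.1.1 show 'Any DLT' for the individual PB2452 groups and All PB2452 only. Mark the placebo and all-subjects cells 'not applicable', with a footnote to the definition in SAP 8.1.6.
2. Add a row 'Any event meeting the DLT grade or withdrawal criteria' for all active and placebo groups, taken from the CTCAE v5 review that the SRC already makes of all adverse events and laboratory abnormalities. State that the row is counted before the causal exclusion and the electrolyte exemption, so that it need not equal 'Any DLT' in the active groups.
3. Reconcile SAP 8.1.6 with SAP 4.4, SAP 13 and protocol amendment 5 on whether grade and cause are judged before or after assignment is known. The SRC's procedure bears on escalation and stopping and is for the sponsor and the SRC to state; this review does not propose one.

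The cost is a few lines of SAP text, one table row and an extension of the SRC spreadsheet. The small downside is that the SRC's CTCAE result must be kept for placebo subjects as well, a quarter of the total. The DLT definition and the escalation and stopping rules are not changed by items 1 and 2.

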8.1.7. Serious Adverse Events

An AE or suspected adverse reaction is considered a SAE/suspected unexpected serious adverse reaction if, in the view of either the investigator or sponsor, it results in any of the following outcomes:

- Death
- Life-threatening AE
- Inpatient hospitalization or prolongation of existing hospitalization
- Persistent or significant incapacity or substantial disruption of the ability to conduct normal life functions
- Congenital anomaly or birth defect

All SAEs and suspected unexpected serious adverse reactions including deaths will be presented in a data listing.

8.2. Clinical Laboratory Evaluations

Blood samples for laboratory safety tests (hematology, coagulation and serum chemistry) and urine samples for urinalysis will be collected at Screening, Day -3 (Cohorts 4 through 10 only), Day -1 (Cohorts 1 through 3 only), Day 3 (Cohorts 1 through 8 and 10 only), Day 4 (Cohort 9 only if a 6th dose of ticagrelor was given on Day 2), Day 7, and Day 28/EOS.

Serology testing will be performed at Screening.

Urine drug, alcohol screen, and Hemoglobin A1C for diabetic patients, will be performed at Screening, Day -3 (Cohorts 4 through 10 only), and Day -1 (Cohorts 1 through 3 only).

Serum pregnancy test for female subjects will be performed at Screening, Day -3 (Cohorts 4 through 10 only), Day -1 (Cohorts 1 through 3 only), and Day 28/EOS.

Stool occult blood test will be performed at Screening for Cohort 10 only.

The following clinical laboratory assessments will be performed:

Hematology: Hematocrit, hemoglobin, mean corpuscular hemoglobin, mean corpuscular hemoglobin concentration, mean corpuscular volume, platelet count, red blood cell count, and total and differential leukocyte count

Coagulation: Activated partial thromboplastin time, international normalized ratio, partial thromboplastin time, and prothrombin time

Serum Chemistry: Alanine aminotransferase, albumin, alkaline phosphatase, aspartate aminotransferase, bicarbonate, bilirubin (total and direct), blood urea nitrogen, calcium, chloride, cholesterol (total, high-density lipoprotein, and calculated low-density lipoprotein), creatine phosphokinase, creatinine, gamma-glutamyltransferase, globulin, glucose, lactate dehydrogenase, magnesium, phosphorus, potassium, sodium, thyroid stimulating hormone (Screening only), total protein, triglycerides, and uric acid

Urinalysis: Appearance, bilirubin, color, glucose, ketones, leukocyte esterase, reflex microscopy (performed if dipstick is positive for protein or blood value of 1+ or greater; and includes bacteria, casts, crystals, epithelial cells, red blood cells, and white blood cells), nitrites, occult blood, pH, protein, specific gravity, turbidity, and urobilinogen

Serology: Hepatitis B surface antigen, hepatitis C virus antibody, and human immunodeficiency virus types 1 and 2 antibodies

Other analyses: Urine drug screen (amphetamines, barbiturates, benzodiazepines, cannabinoids, cocaine, cotinine, methylenedioxymethamphetamine, opiates, phencyclidine, propoxyphene, and tetrahydrocannabinol), urine alcohol. Follicle-stimulating hormone and serum pregnancy test (human chorionic gonadotropin) will be collected for female subjects.

The investigator will determine whether any of the abnormally high or low results are clinically significant or not clinically significant.

The hematology and coagulation, chemistry, and urinalysis test results will be presented in the data listings sorted by treatment group, subject, laboratory test, and sample collection date/time. Values that are outside of the normal range as well as the clinically significance information will be flagged in the listings. Actual results and change from baseline will be summarized for the safety population. Refer to [Section 4.1](#) for the definition of baseline for this summary. Shift tables will be generated for the safety population.

All other laboratory tests will be presented in a data listing sorted treatment group, subject, laboratory test category, laboratory test, and sample collection date/time.

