2.2. Secondary

The secondary objectives of the study are:

- To determine the PK of ascending doses of IV MEDI2452 (PB2452) in the presence and absence of ticagrelor
- To determine the PK of ticagrelor and its active metabolite AR-C124910XX in the presence and absence of MEDI2452 (PB2452)

- To assess the effectiveness of a single IV MEDI2452 (PB2452) dose in reversing ticagrelor antiplatelet activity by measuring P2Y₁₂ reaction units (PRU) with VerifyNow™ P2Y₁₂ assay and platelet reactivity index (PRI) with vasodilator stimulated phosphoprotein (VASP) phosphorylation assay by enzyme-linked immunosorbent assay (ELISA)
- To evaluate the PK and PD of restarting a single dose of oral ticagrelor 24 hours after MEDI2452 (PB2452) administration if a sixth dose of ticagrelor is given
- To evaluate the immunogenicity potential of MEDI2452 (PB2452)

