Urine alcohol	X	X ^c			X ^d					
Serum pregnancy test	X	X ^c			X ^d					X
Serology testing	X									
Admission to clinic		X ^c			X ^d					
Physical examination ^e	X	X ^c			X ^d			X		X X
Vital sign measurements ^f	X	X ^c			X ^d	X	X	X	X	X X
12-lead electrocardiogram ^g	X					X	X	X		X X
Cardiac telemetry monitoring ^h		X			X	X	X	X		
Clinical laboratory testing	X	X ^c			X ^d			X		X X
Randomization						X				
Drug administration										
Ticagrelor			X ⁱ	X ⁱ	X ⁱ					
MEDI2452 (PB2452)/Placebo ^k					X					
PK blood sampling ^l										
Plasma MEDI2452 (PB2452) ^l					X	X	X	X ^{aa}	X	X
Plasma ticagrelor/AR-C124910XX ^l					X	X	X ^x	X		
Free plasma ticagrelor/AR-C124910XX ^l					X	X	X ^x	X		
PK urine sampling ^q			X		X	X	X			
PD sampling (LTA/PRU/VASP) ^r			X		X	X	X			
Infusion site assessment ^t					X	X	X	X	X	
Serum immunogenicity		X ^c		X ^d					X	X ^w
Adverse events		X ^c	X ^c	X	X	X	X	X	X	X
Discharge from clinic								X ^u	X	

Abbreviations: BID, twice daily; EOS, end-of-study; FU, follow-up; LTA, light transmittance aggregometry; PD, pharmacodynamic; PK, pharmacokinetic; PRU, P2Y₁₂ reaction units; VASP, vasodilator stimulated phosphoprotein.

- ^a Follow-up visits will be conducted as outpatient.
- ^c Cohorts 4 through 10 only.
- ^d Cohorts 1 through 3 only.
- ^e Full physical examination (including height, weight, and body mass index calculation) will be performed at screening and Day 28 only. Brief physical examinations will be performed at all other time points.
- ^f Vital sign measurements (systolic and diastolic blood pressures, oral body temperature, respiratory rate, and heart rate) will be collected at screening, check-in, before dosing (30 minutes prior to the initiation of the study drug infusion) and at 0.5, 0.75, 1, 2, 4, 8, and 24 hours after the initiation of the study drug infusion, and at 30, 36, 42, and 48 hours after the initiation of the study drug infusion and on Days 4, 7, and 28. Starting with the 1 hour after initiation of the study drug timepoint for the collection of vitals a ±5 minute window will be permitted. During the initial 30 minutes of study drug infusion, systolic and diastolic blood pressures and heart rate will be collected every 5 minutes.

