- ^g Electrocardiograms will be obtained in triplicate for all subjects at screening, before dosing (within 1 hour prior to the initiation of the study drug infusion) and at 1 (±10 minutes), 4 (±10 minutes), 5 (±10 minutes), 24 (±30 minutes), and 48 hours (±30 minutes) after the initiation of the study drug infusion and on Days 7 and 28.
- ^h Cardiac telemetry monitoring will begin on Day -1 approximately 12 hours prior to the initiation of the study drug infusion (Hour 0) and will continue until the subject is discharged from the clinical site for Cohorts 1-10. For Cohorts 4-10, cardiac telemetry monitoring will begin on Day-3 (check in) approximately 12 hours prior to the first dose of Ticagrelor and will be removed once dosed with the initial dose of Ticagrelor.
- ⁱ For Cohorts 4 through 6 only: Beginning in the morning on Day -2, ticagrelor will be administered as a single oral dose of 180 mg, followed by 90 mg every 12 hours for 4 additional doses through Hour 0 (i.e., 5 total doses of ticagrelor). For Cohorts 7 through 10 only: Beginning in the morning on Day -2, ticagrelor will be administered as a single oral dose of 180 mg, followed by 90 mg every 12 hours for 4 additional doses through to Hour -2 (two hours prior to dosing at Hour 0) (i.e., 5 total doses of ticagrelor).
- ^k For all cohorts: MEDI2452 (PB2452) or placebo will be administered at Hour 0 of Day 1.
- ^l For timing of pharmacokinetic plasma samples for each cohort, refer to [section 3.5.1](#) of the protocol.
- ^q For Cohorts 4 through 10 only: Urine samples for PK analysis of ticagrelor and AR-C124910XX concentrations will be collected before dosing (within 60 minutes prior to the first ticagrelor dose on Day -2), and 0 to 6, 6 to 12, 12 to 24 and 24 to 48 hours after the initiation of the study drug infusion.
- ^r For timing of pharmacodynamic samples for each cohort, refer to [section 3.5.2](#) of the protocol.
- ^t Infusion site assessments will be performed for all subjects within 15 minutes prior to the initiation of the study drug infusion (Hour 0), and at 1, 3, 24, 48, and 72 hours after initiation of the study drug infusion and on Day 7.
- ^u For Cohorts 1 through 8 only.

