8.5. Physical Examination and Physical Measurements

Full physical examination (including height, weight, and BMI calculation, assessment of skin, head, ears, eyes, nose, throat, neck, thyroid, lungs, heart, cardiovascular, abdomen, lymph nodes, and musculoskeletal system/extremities) will be performed at screening and Day 28 only. Brief physical examinations will include assessment of skin (including any signs for cutaneous erythema), lungs, cardiovascular system, and abdomen (liver, spleen) and will be performed at Day -3 (Cohorts 4 through 10 only), Day -1 (Cohorts 1 through 3 only), Day 3, and Day 7.

Interim physical examinations will be performed at the discretion of the investigator, if necessary, to evaluate AEs or clinical laboratory abnormalities.

Physical examination data will be listed. Screening height, weight and BMI will be summarized together with demographics variables.

9. Immunogenicity Analysis

Immunogenicity (antibody) samples will be screened for the presence of binding anti-drug antibody (ADA) on Day -3 (Cohorts 4 through 10 only), Day -1 (Cohorts 1 through 3 only), Day 7, and Day 28/EOS. A subject testing positive for ADA at the final planned visit (Day 28) will be asked to return for follow-up sampling approximately 3 months after their final visit and approximately every 6 months thereafter until these no longer test positive or until levels return to a pre-dose state.

The ADA result (positive or negative) will be summarized by treatment group and visit using counts and percentages. All ADA results with corresponding titer values will be presented in a data listing. The neutralizing antibody (NAb) results may be listed and summarized in the clinical study report if the assay is available.

10. Pharmacokinetic Analysis

The PK population will be used for all PK analysis tables and figures.

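### SAP Section 8.2 and SAP Table 3-2 contradict each other on Cohort 9 laboratory testing; under Section 8.2, without a sixth ticagrelor dose, nothing is scheduled between Day -3 and Day 7

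*SAP*

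**What the plan says.** SAP Section 8.2 lists the laboratory days by cohort. Check-in tests are on "Day -3 (Cohorts 4 through 10 only), Day -1 (Cohorts 1 through 3 only". The early post-dose test is on "Day 3 (Cohorts 1 through 8 and 10 only", which excludes Cohort 9. Cohort 9's own entry is "Day 4 (Cohort 9 only if a 6th dose of ticagrelor was given on Day 2". Days 7 and 28 apply to every cohort.

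SAP Table 3-2 has a row for "Clinical laboratory testing". Between check-in and Day 7 it carries one mark, in the Day 3 column, with no cohort footnote. Day 4 is blank in that row.

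On ticagrelor, footnote i to Table 3-2 takes Cohorts 7 to 10 "through to Hour -2 (two hours prior to dosing at Hour 0) (i.e., 5 total doses of ticagrelor". A sixth dose appears only as a conditional: in Section 8.2, and in the Section 2.2 objective on restarting ticagrelor after PB2452 "administration if a sixth dose of ticagrelor is given".

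On toxicity, Section 8.1.6 states: "A DLT is defined as any grade 2 or higher laboratory abnormality" in a subject confirmed to have received active drug. Section 13 requires a blinded safety review of each cohort before the next is dosed.

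**The concern.** Section 8.2 has no clause for Cohort 9 without a sixth ticagrelor dose, and that is the case the SAP's own dosing footnote schedules. Followed as written, the cohort goes from check-in to Day 7 with no scheduled laboratory sample. Table 3-2 shows one on Day 3.

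Two things are at stake. The first is safety information: Cohort 9 receives 18000 mg, the top dose in the plan, and laboratory abnormalities of grade 2 or higher count as dose-limiting toxicities. The second is the analysis. Section 4.6 keeps results that do not come from a scheduled event out of the summary tables, except for determining baseline. If Cohort 9 was sampled on Day 3 under Table 3-2, a programmer following Section 8.2 could treat those values as unscheduled and leave them in the listings only.

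**Working it through.** No power or error-rate calculation applies. The check compares the two schedules.

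**Confirming the Day 3 column.** Table 3-2 was read as extracted text, so the column was checked in two ways.
- The vital signs row has marks on Days 1, 2, 3, 4, 7 and 28, as SAP Section 8.3 requires. The single mark in the laboratory row sits in the same position as the third of these, Day 3.
- The laboratory row has the same layout as the physical examination row. Section 8.5 says the brief examinations are "performed at Day -3 (Cohorts 4 through 10 only), Day -1 (Cohorts 1 through 3 only), Day 3, and Day 7".

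**Number of ticagrelor doses.** Footnote i gives one loading dose plus four further doses, five in total. The ticagrelor row in Table 3-2 carries only footnote i. Footnote j, which in Table 6-1 of the supplied protocol held the Day 2 sixth dose, is among those the SAP says are intentionally omitted. So no sixth dose is the scheduled case, and a sixth dose is the exception.

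**Laboratory days after screening.** Dosing every 12 hours from the morning of Day -2 puts the fifth dose 48 hours later, on the morning of Day 1, so there is no Day 0. The gap from Day -3 to Day d is therefore 3 + (d - 1) = d + 2 days.

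| Cohort and source | Laboratory days | First post-dose day | Gap from check-in |
|---|---|---|---|
| 9, Section 8.2, no sixth dose | -3, 7, 28 | 7 | 7 + 2 = 9 days |
| 9, Section 8.2, sixth dose given | -3, 4, 7, 28 | 4 | 4 + 2 = 6 days |
| 9, Table 3-2 | -3, 3, 7, 28 | 3 | 3 + 2 = 5 days |
| 8 and 10, Section 8.2 and Table 3-2 | -3, 3, 7, 28 | 3 | 5 days |

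Section 8.2 and Table 3-2 agree for Cohorts 8 and 10. For Cohort 9 they differ in both cases: Section 8.2 gives either no early test or a Day 4 test, and Table 3-2 gives Day 3.

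**Unobserved interval.** Section 7.3 gives the Cohort 9 infusion as 15 min + 4 h + 12 h 5 min = 16 h 20 min, or about 0.7 day. Day 7 is nominally 6 days after the infusion starts, so about 6 - 0.7 = 5.3 days after it ends.

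**Subjects affected.** Table 3-1 gives 4 subjects (3 active, 1 placebo), with the option of 4 more in the same ratio: 8 (6 active, 2 placebo).

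**Logistics.** SAP Section 3 keeps Cohorts 9 and 10 in-house through Day 4. Subjects are in the clinic on both candidate days, so attendance does not explain the omission.

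**The case against.** A reader might infer that laboratory dose-limiting toxicities would be undetectable in Cohort 9. The documents do not support that. Days 7 and 28 remain scheduled. Protocol Section 3.5.5 allows repeat tests at the investigator's discretion and has clinically significant changes documented on the adverse event page. The toxicity outputs come from the safety review committee's own spreadsheet (SAP Section 8.1.6), not from the Section 8.2 visit list.

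Nor does any passage say that Section 8.2 alone defines the visits in the laboratory tables. Table 3-2 is in the same SAP, so a Day 3 sample taken under it can fairly be called scheduled, and a Day 3 row would exist for the other cohorts anyway. Exclusion under Section 4.6 is a risk created by the contradiction, not a demonstrated loss.

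A third inference is that the longest regimen has no early laboratory data at all. Cohort 10 has the same regimen and keeps its Day 3 tests in Section 8.2.

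The 24-hour electrolyte exemption in Section 8.1.6 does not single out Cohort 9 either. One early sample followed by Day 7 cannot show resolution within 24 hours in any cohort.

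Table 3-1 and Section 7.3 are weak evidence on a sixth dose: the first covers only ticagrelor given before the infusion, and the second covers PB2452 or placebo. The point rests on footnote i.

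The strongest objection is that the governing protocol was not available. The SAP reflects amendment 5 of 03 August 2018. The supplied protocol is dated 01 February 2018, and its Cohort 9 was a different design with a planned Day 2 ticagrelor dose. What was collected may follow amendment 5 whatever Section 8.2 says. This limits the claim about conduct, but it does not remove the contradiction inside the SAP.

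**Conclusion.** The contradiction holds. For Cohort 9, Section 8.2 and Table 3-2 give different early post-dose laboratory days whether or not a sixth dose is given. In the five-dose case that the SAP schedules, Section 8.2 gives none before Day 7.

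The consequence concerns 4 or 8 subjects, of whom the 3 or 6 on active drug can count towards a dose-limiting toxicity. If Section 8.2 was followed and no sixth dose was given:
- scheduled sampling would miss a grade 2 or higher laboratory abnormality that arose after dosing and resolved before Day 7;
- a safety review held after Day 4 would have no scheduled post-dose laboratory data for this cohort.

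The second consequence assumes that amendment 5 keeps the Day 4 review timing of supplied protocol Section 3.4.2.4. If Table 3-2 was followed instead, the samples exist and the remaining risk is their treatment in the summary tables. The documents do not show which schedule was followed.

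**What to change.** Reconcile SAP Section 8.2, SAP Table 3-2 and protocol amendment 5. State Cohort 9's laboratory days explicitly for both cases, with and without a sixth ticagrelor dose. State which early post-dose visit is used for Cohort 9 in Tables 14.3.4.1.x and 14.3.4.2.x, so that Section 4.6 cannot be applied to those samples by accident. Which day is correct is for the sponsor to settle from amendment 5.

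If collection followed Table 3-2, this is a change of SAP wording only. If collection followed Section 8.2 and no sixth dose was given, wording cannot supply the missing values, and the report should say that Cohort 9 has no scheduled laboratory data between Day -3 and Day 7.
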